(AWARE): A Stage IA and IB Intervention Development Study to screen at least 400 women in the greater Boston area and recruit a total of 96 women who meet the criteria for PTSD and traumatic history. The 8-week intervention will be given group psychotherapy along with secure mobile messages. Adherence to group psychotherapy, utilization/satisfaction of text messages, and safety (suicidality and intimate partner violence) will be tested as feasibility outcomes. The efficacy will also be tested by measuring HIV-related outcomes and psychiatric symptoms and substance use at baseline, week 8, and 3 months to determine effect of the adapted intervention. There will be a Focus Group Feedback Discussion after the 8-week psychotherapy sessions to allow participants to comment on the effectiveness of the intervention. This integrative approach is innovative in multiple ways: (1) the study will be the first pilot RCT study to target traumatized API women, (2) it feasibly incorporates a culturally appropriate intervention, (3) it is designed to reduce HIV risk behavior, and (4) it tests the feasibility of mobile technology. It is our aim that these efforts will ultimately lead to the reduction of HIV transmission, suicidality, and psychiatric symptoms among API women.

Section D: Background/ Rationale/ Purpose

In the text box below provide the following study information

- Background information
- Study rationale
- Study objectives and/or hypotheses

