3. Low reporting rates and under-utilization of treatment for traumatized API women. API women who were victims of sexual assault are particularly vulnerable. API women may experience higher levels of psychological distress or have fewer adaptive coping skills/social supports compared to sexually-victimized White women.³³ Rau and Diclemente found that API parents of sexual victims provide less support and minimal involvement in helping victims to seek evaluation and treatment with the appropriate services.³⁷ Our AWWHIP study showed that the experience of child sexual abuse combined with other types of abuse was the most powerful and robust predictor of severe depression, suicidal ideation, and suicide attempts.²⁶

Study objectives and/or hypotheses: The aim for *year one* is to adapt an intervention for API women that reduces HIV risk behaviors while increasing HIV knowledge and self-efficacy in negotiating safer sex (primary outcomes) and reduces psychiatric symptom severity and substance use (secondary outcomes). During *year 2*, the feasibility and safety of stage 1B of the AWARE intervention will be established through a pilot RCT, in which an intervention group will receive AWARE (n=48), which will have adapted SS by integrating Project FIO and

cultural components. During *years 2 and 3*, the preliminary efficacy of the intervention for API women will be tested.

It is hypothesized that the AWARE intervention group will significantly exceed the wait-list group in reduction of HIV risk behaviors and increased HIV knowledge and self-efficacy in negotiating safer sex at the 8 weeks and 3 months post-test points (primary outcomes). Additionally, the AWARE intervention group will significantly exceed the wait-list group in reduction of PTSD symptoms (and/or other mental health outcomes) and the frequency of substance use (at 8 weeks and 3 months post-test) (secondary outcomes).

Section E: Study subjects

E. 1. Gender

Select gender of subjects: ___ male female ___ both

E. 2. Age

Age range of subjects: (check all categories that apply to any of the subjects)

- Adults (18 years and older)
 Infants (< 1 year)
 Young children (1-6 years of age)
 Children 7-11 years
 Adolescents (12-17 years of age)

E. 3. Race/ Ethnicity (check all that apply)

- Mixed race or ethnicity
 American Indian or Alaskan Native
 Asian or Pacific Islander
 Black (not of Hispanic Origin)
 Hispanic
 White (not of Hispanic Origin)

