In Year 1 (the intervention development phase), we will begin recruiting and screening participants from AWARE. The first 10 women who pass the eligibility screenings and agree to participate the study will be invited to participate as members of the Asian Women Discussion Group, which will serve as a focus group. Although we will administer our preliminary AWARE intervention to the ten selected participants, there is no experimental intervention for the Asian Women Discussion Group. The sole purpose of this focus group is for members to give feedback from the perspective of AWARE intervention participants (as both the Asian Women Discussion Group and the AWARE group must meet the same demographic and clinical criteria). Members in this focus group will be ineligible to participate in the AWARE intervention group (Phase 2 of the study). Members in the Asian Women Discussion Group will attend 10 psychotherapy sessions and an additional discussion meeting afterward, as well as an additional session in September.

2) *AWARE intervention group*

In Year 2 of our study, using Asian Women Discussion Group’s feedback and other revisions made during the intervention development phase (in Year 1), we will administer our improved AWARE intervention (Stage IB) to 48 randomly-selected eligible participants. Participants in this group will receive 8 consecutive weekly sessions to receive the manualized intervention. After the last session, participants will be scheduled to return for a 3-month follow-up.

3) *Wait-list (or, delayed treatment) group*

Also in Year 2, the wait-list group will receive the exact same intervention 3 months *after* the start of the AWARE intervention group. The wait-list group will be comprised of 48 randomly-selected eligible participants.

Detailed Procedure:

1. In Year 1, for recruitment of Asian Women Discussion Group participants, we will use first use the database of 720 women who participated in the PI’s prior study (AWSHIP).

We will randomly select approximately 100 AWWSHIP women (who previously indicated interest in future studies) and ask them to participate in the initial eligibility screening. The function and purpose of Asian Women Discussion Group will be described to each woman by phone, letter, or email.

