6. In Year 2, we will recommence our recruitment efforts to identify and enroll eligible women into the intervention group and the wait-list group. The interviews during the screening process will be audio-recorded. Women who will be screened in Year 2 go through the same process as women who screened in Year 1 for Asian Women Discussion Group and must meet the same eligibility requirements (see Step 2 and Step 3).
7. Our goal is to screen about 400 women in Year 2. Of this number, we expect about 30% (n=120) to meet all eligibility criteria. We will randomly select 96 eligible women and assign 48 to the AWARE intervention group and 48 to the wait-list group.
8. Individual participation in the AWARE intervention group includes:
 - a. Written consent to participate including consent for the audiotaping of each session.
 - b. Completion of a baseline assessment prior to the start of the group sessions.
 - c. Participation in 105-minute group sessions each week (for a total of 8 weeks) with a small group of other participants and a clinician, covering topics including: Safety, Taking Good Care of Yourself, Compassion, Commitment, Creating Meaning, Setting Boundaries in Relationships, Coping with Triggers, Healthy Relationships, Self-Nurturing, and The Life Choices Game
 - d. \$26 payment and \$4 transportation reimbursement for each weekly group session and \$20 payment and \$4 transportation reimbursement for each assessment.
 - e. Completion of a weekly Adverse Events Log and a weekly questionnaire on the AWARE stories.
 - f. Receipt of and response to daily, secure mobile text messages (called “AWARE Stories”) in between each weekly session to reinforce participation and adherence
 - g. Completion of assessments upon the last intervention session
 - h. Completion of outcome assessments in a follow-up visit 3 months after the last intervention session
9. Individual participation in the wait-list group includes:
 - a. Written consent to participate including consent for the audiotaping of each session.
 - b. Completion of a baseline assessment prior to the start of the group sessions.
 - c. Participation in 90-minute group sessions each week (for a total of 8 weeks plus an additional post-intervention meeting) with a small group of other participants and a clinician, covering topics including: Safety, Taking Good Care of Yourself, Compassion, Commitment, Creating Meaning, Setting Boundaries in Relationships,

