Coping with Triggers, Healthy Relationships, Self-Nurturing, and The Life Choices Game

- d. \$26 payment and \$4 transportation reimbursement for each focus group session and \$20 payment and \$4 transportation reimbursement for each assessment.
- e. Completion of a weekly Adverse Events Log and a weekly questionnaire on the AWARE stories.
- f. Receipt of and response to daily, secure mobile text messages (called “AWARE Stories”) in between each weekly session to reinforce participation and adherence.
- g. Completion of assessments upon the last intervention session.
- h. Completion of outcome assessments in a follow-up visit 3 months after the last intervention session.

F.5. Primary outcomes

Indicate in the box below anticipated primary and secondary outcomes if applicable

Primary outcomes: decrease in HIV risk behaviors, increase in HIV knowledge, increase in self-efficacy in negotiating safer sex

Secondary outcomes: decreased psychiatric symptom severity and decreased substance use

F.6. Surveys, interviews, questionnaires, etc.

You must attach to this application all surveys, interviews, questionnaires, focus group outlines, etc. that will be used in this study. The IRB must review these materials as part of its review.

Failure to provide this information could result in a delay in IRB review. If some of the materials are not finalized- submit the DRAFT versions. The final versions will need to be approved by the IRB via an amendment PRIOR to use.

I have attached all surveys, interviews, questionnaires, data collection forms that will be used in this study

Section G: Sample Size /Data Analysis

G. 1. Sample Size

Indicate in the box below how many subjects you anticipate will be enrolled in this study (or how many records you will review). If this protocol involves more than one cohort or study phase please specify anticipated sample size for each cohort /study phase. If this study involves multiple experiments you may attach a table summarizing anticipated enrollments by experiment and subject category.

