Evaluation of Pilot RCT Analysis: We will use an intention-to-treat (ITT) analysis, which indicates all women who are randomized will be included for analysis. To test the success of the randomization, prognostic factors including baseline education, psychiatric diagnosis severity, and substance use will be compared between participants in the intervention group and wait-list group using chi-square tests. Baseline characteristics that show imbalance between groups will be adjusted in multivariate regression models. The efficacy outcome variables will be analyzed as either dichotomized or continuous variables. For PTSD, continuous measures of the CAPS will be assessed. In order to sensitively capture any changes in PTSD scores, continuous measure will be chosen. For HIV outcomes, we will use both dichotomous and continuous variables to measure status and severity of the outcomes at baseline, 8 weeks, and 3-month post-test. Mixed effects models will be used to compare the pattern of change in dichotomous and continuous outcomes over time between groups using normal and logit links, respectively. We will first use an unstructured covariance matrix to

account for correlation between repeated measurements in the same participant and compare it to other covariance structures, using goodness of fit. The most suitable covariance matrix will be chosen for the final model. The same approach will be followed for secondary outcomes. All statistical testing will be performed at the significance level of 0.05 using SAS 9.3.102. Additionally, in order to explore whether compliance affects outcome measures, we will compare the sexual risk behavior, psychiatric severity, and substance use measures between those who drop out versus those who complete the intervention using two-tailed, independent samples t-tests.

Data analysis for Aim 3 (year 2 and 3):

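### At AWARE's follow-up, 3 months after its last session, the wait-list arm has had 7 or 8 of its 8 sessions, so the 3-month between-arm hypothesis has no untreated control

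*Protocol*

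**What the plan says.** **When treatment is given.** Section F.4 gives the AWARE arm 8 consecutive weekly sessions. For the other arm it states that "the wait-list group will receive the exact same intervention 3 months *after* the start of the AWARE intervention group".

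**When AWARE is followed up.** The F.4 overview says "After the last session, participants will be scheduled to return for a 3-month follow-up". Item 8h of the detailed procedure is explicit: "Completion of outcome assessments in a follow-up visit 3 months after the last intervention session". Item 9h gives the wait-list arm the same rule relative to its own last session.

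**What is claimed at that visit.** Section D hypothesises that AWARE will significantly exceed the wait-list group in reducing HIV risk behaviours, with "increased HIV knowledge and self-efficacy in negotiating safer sex at the 8 weeks and 3 months post-test points (primary outcomes"). It names the same two time points for the secondary outcomes. Section G.3 adds "Mixed effects models will be used to compare the pattern of change in dichotomous and continuous outcomes over time between groups", with measurements at baseline, 8 weeks and 3 months.

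**How the control is described.** Section G.1 describes the wait-list arm as receiving no treatment.

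**Where the anchor is missing.** The Section C summary measures "substance use at baseline, week 8, and 3 months to determine effect of the adapted intervention" without saying what the 3 months are counted from.

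**What the wait-list arm is assessed on.** Item 9 lists "Completion of a baseline assessment prior to the start of the group sessions", then "Completion of assessments upon the last intervention session", then the visit 3 months later. It does not clearly place an outcome assessment at calendar week 8, although Sections D, E.5.B, G.3 and L.2 imply one.

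**The concern.** A wait-list arm is a control only while it waits. Here the wait is counted from AWARE's first session and the follow-up from AWARE's last, so the wait ends well before the follow-up. One of the two time points in the primary hypothesis therefore compares treated women with treated women.

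Two things are at stake. An effect that is present and lasting could be reported as lost at follow-up, simply because the comparison arm has caught up. In addition, Section D says the efficacy outcomes are meant to help plan a larger study. A 3-month difference from this schedule would be a poor input, because it does not measure the effect of AWARE against its absence. Untreated data cannot be collected from the wait-list women once their sessions have begun, so an analysis plan cannot repair this later.

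**Working it through.** The protocol gives no figure to reproduce: G.2 states that no formal sample size calculation was made. The check is calendar arithmetic on the protocol's own intervals.

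**Inputs**
- 8 weekly AWARE sessions (F.4): days 0, 7, …, 49.
- AWARE follow-up (item 8h): last session + M, where M is the length of 3 months in days.
- Wait-list sessions (F.4 overview and item 9c): 8 weekly sessions from day M, so the last is on day M + 49.

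**General result.** Let L be the time from first to last session. AWARE follow-up = L + M, and the last wait-list session = M + L. The two dates coincide whatever L and M are. The 10-session wording in G.1 therefore does not help: the overlap becomes 9 to 10 of 10.

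**Numbers**

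| M (days) | AWARE follow-up, 49 + M | Wait-list sessions run | Given before that day | On or before |
|---|---|---|---|---|
| 84 | day 133 | 84–133 | 7 | 8 |
| 89 | day 138 | 89–138 | 7 | 8 |
| 91 | day 140 | 91–140 | 7 | 8 |
| 92 | day 141 | 92–141 | 7 | 8 |

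- Counted from the end of week 8 (day 56 + M), all 8 sessions are done before the follow-up.
- With true calendar months and every start date in a year, the count is 7 or 8.
- With M = 91 and a visit one or two weeks early, 7 or 6 sessions have been given.
- If the wait-list value is taken from that arm's own visit (item 9h), it falls on day 2M + 49, which is day 231 for M = 91. All 8 sessions are then complete and both arms are 3 months past treatment.
- The week-8 time point (day 49 to 56) precedes the wait-list start (day 84 to 92), so that contrast keeps an untreated control.

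**Illustration of the consequence.** The effect sizes, full maintenance of benefit and linear build-up over sessions are assumptions; none is in the protocol. G.3 expects 15% loss by week 8 and another 5% at the 3-month visit: 48 × 0.80 = 38.4, so 38 per arm. The test is a two-sided t-test at 0.05.

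| Maintained effect (SD) | Power against an untreated control | Difference left with 7 of 8 sessions given (effect × 1/8) | Chance of significance |
|---|---|---|---|
| 0.3 | 25% | 0.04 | 5% |
| 0.5 | 58% | 0.06 | 6% |
| 0.8 | 93% | 0.10 | 7% |

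With all 8 sessions given and full catch-up, the expected difference is 0 and the chance of significance is the 5% error rate.

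**The case against.** **The anchor is less settled than the arithmetic suggests.** Sections C, D (design summary), E.5.B, G.3 and L.2 list the visit beside week 8 with no stated origin. The F.4 overview sentence could describe when the visit is booked rather than when it falls. Item 9h anchors the wait-list arm's visit, not AWARE's. A visit 3 months from AWARE's start would coincide with the wait-list start and fit the untreated control in G.1. All of this is fair, but item 8h is explicit for AWARE, and the post-test wording in Section D points the same way. If the from-start reading was intended, item 8h is wrong and must still be corrected.

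**The late comparison is still randomised.** F.4 also calls the arm delayed treatment, and immediate against delayed treatment is a legitimate contrast. That stands. It is not the contrast described in G.1, however, and superiority at that date is not what such a contrast would be expected to show.

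**The direction of error is conditional.** If AWARE's effect fades, the difference could be negative. If reported behaviour lags or the recall period reaches back into the waiting time, it may not be zero. This also stands, and it is why the power figures are only an illustration. The session count needs none of these assumptions.

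**This is a pilot centred on feasibility and safety.** True, and week 8 is unaffected. Section D nonetheless states the 3-month contrast as a primary hypothesis.

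**Conclusion.** The concern holds. On the schedule as written, 7 or 8 of the 8 wait-list sessions have been delivered by AWARE's follow-up, for any course length and any reasonable length of 3 months. The 3-month hypothesis in Section D, and the part of the G.3 model that uses that visit, cannot estimate AWARE against no AWARE. The description of the control in G.1 is true only of the waiting period.

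The conclusion rests on item 8h meaning what it says. An expected difference near zero rests further on maintained benefit and full catch-up by the wait-list arm.

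The defect is confined to the late visit. The gap in item 9 over a wait-list assessment at week 8 needs reconciling, but it does not show that the week-8 contrast is lost.

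**What to change.** **Required**
- Reconcile Sections C, D, F.4 (overview and items 8 and 9), G.1 and G.3 on what the 3 months are counted from, when wait-list women are assessed, and the period for which that arm is untreated.
- Anchor outcome assessments in both arms to randomisation or to AWARE's start date, and state that wait-list women complete the outcome battery at calendar week 8.
- Make week 8 the randomised between-arm comparison.
- Withdraw the treated-versus-untreated claim at 3 months after the last session. Report those data as within-arm maintenance, or label the comparison openly as immediate against delayed treatment. Keep wait-list data collected after that arm starts its sessions out of the untreated control series.

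**Optional**
- If a later untreated comparison is wanted, assess both arms at month 3 from AWARE's start, before the first wait-list session.

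**Cost.** The required part is mainly protocol wording. At the F.4 rates of $20 plus $4 per assessment, one added wait-list assessment costs at most 48 × $24 = $1,152 in participant payments, and two cost $2,304. L.2 already lists an 8-week evaluation. The optional month-3 visit in the AWARE arm adds at most another $1,152. Assessor time is extra, since the battery includes a structured PTSD interview and a suicidality scale that needs a trained administrator. The sponsor gives up a late between-arm claim that the design cannot support.

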Background information: The proposed 3-year adaptation and pilot testing of the Asian Women’s Action for Resilience and Empowerment (AWARE): A Stage IA and IB Intervention Development Study consists of the following goals: (1) provide the original Seeking Safety (SS) ¹ curriculum to Asian Women Discussion Group members for feedback and revision; (2) fully develop the AWARE protocol (which will modify SS by integrating Project FIO² and our cultural component) for API women; (3) use a pilot two-armed RCT design to test the feasibility and safety of our adapted intervention in Year 2, comparing the AWARE intervention group (n=48) with the wait-list group (n =48); and (4) employ multiple measures of the same constructs using a repeated measures design (assessments at pre-test, 8 weeks, and 3-month follow-up). We chose an RCT design to (1) establish the validity of statistical testing to the maximum level and (2) minimize potential biases (known and unknown factors and characteristics of the intervention and control groups). We will obtain outcomes for feasibility, safety, and preliminary efficacy of the primary outcomes (HIV-related outcomes) and secondary outcomes (psychiatric symptoms, substance use). These feasibility, safety, and efficacy outcomes will allow us to better plan for a larger-powered study. We will conduct the focus groups and pilot RCT at Boston University, School of Social Work (BUSSW), MA.

Study rationale and significance: *There is a mental and sexual health crisis in the API community in the US, particularly among young women (ages 18-35). This proposed*

project is intended to deepen our national understanding of this crisis and move us toward highly innovative solutions. We propose to design an appropriate intervention that reduces mental and sexual health problems in this population. There are 3 significant reasons why this study should be funded for research:

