16. “I can relate to this quote; I used to have similar responses. I used to find pleasure in harming myself. I used to cut myself for a long time.” **Response:** Thank you for sharing your experience. It is possible that many other group members have had similar experiences. It may be useful to you and the group to share your story.

17. “I just don’t feel worthy as person, no one is ever going to love me or care about me.” **Response:** We recognize that these are strong emotions. If you feel comfortable, we recommend that you share these thoughts with the group. The therapist will call you this week to check in.

18. “I can really relate to that—I have trouble setting boundaries in relationships...People walk all over me; I’m weak.” **Response:** We think you are a very strong person for openly talking about your feelings and emotions. We encourage you to share your response with the group next session.

19. “The sessions are becoming very stressful for me; I find myself feeling upset when I leave.” **Response:** Thank you for sharing this. We want to do whatever we can to make this a more positive experience. The therapist will call you this week to check in.

20. “I can relate to this quote, I don’t know what’s to become of my future...I am a complete failure.” **Response:** Thinking about the future can evoke uncertain feelings. Others may be experiencing similar feelings; it may be valuable for you to address these concerns in the session.

Adverse Events

This study carries some risk for the development of suicidal ideation, suicide attempts, and self-mutilation as adverse events because the women eligible to participate have PTSD or a history of violent trauma. In order to address this risk, we will evaluate potential development of these adverse events at baseline, 8 weeks, and the 3-month follow-up, as well as informally monitoring participant condition on a weekly basis. Participants in the wait-list group will also be assessed for adverse events over the phone at 3 weeks and 6 weeks after the start of treatment for the intervention group. Participants will also be asked to keep a Weekly Adverse Event Log to

measure safety outcomes. In addition, since our screening measures may detect suicidal risk and intimate partner violence, we will also provide appropriate care as necessary. We will use the following assessments to assess risk:

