Quantitative data for protocol evaluation and participant psychometric monitoring: We will evaluate participants in the Asian Women Discussion Group by comparing the results of pre-intervention and post-intervention psychometric measures. These comparisons will be used to determine if the current protocol is achieving the intervention's goals of providing benefits to participant's mental and behavioral health.

Data Analysis for Aim 2 (year 2):

(1) Feasibility Analysis of group psychotherapy: We conservatively anticipate that 15% of participants will dropout during the 8 week RCT. We also anticipate that another 5% will dropout at the 3-month follow-up evaluation. The first stage of analysis will involve estimating the proportion of women who are eligible and agree to enroll in the study. A 95% confidence interval for the proportion will also be produced. Then, among those who enroll, baseline characteristics will be compared between those randomized to the intervention and those randomized to the wait-list control group to assess balance.

We will estimate the proportion of women who adhere at 8 weeks and 3-month follow-up. Mean proportion of women who attend (at 8 weeks and 3-month follow-up) and 95% confidence intervals will be generated for the total sample and then by groups. We will test the

difference between the participants' adherence rates in the intervention and control group at 8 weeks and 3-month follow-up using a chi-square test. We will then examine bivariate associations between baseline characteristics and attrition (each time point considered separately) using chi-square tests for categorical variables and two sample t tests for continuous variables among all participants. Multivariable associations will be examined using multiple logistic regression models for adherence by group, relating those characteristics that were significant in bivariate analysis to attrition, if sample size permits.

(2) Feasibility Analysis of AWARE Stories (Hypothesis for secure mobile messaging): Higher level of satisfaction and higher utilization of secure text messages are positively associated with group psychotherapy attendance. Ordinal chi-square tests will be used to examine the association between ordinal scale (1-4) of messaging satisfaction and utilization questions and psychotherapy attendance.]

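### Outcome visits in both arms hang on the last intervention session, and nothing says that women who stop attending are still assessed at 8 weeks and 3 months

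*Protocol*

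**What the plan says.** **Visit steps (Protocol F.4, Detailed Procedure).** For the AWARE arm, step 8g is "Completion of assessments upon the last intervention session" and step 8h is "Completion of outcome assessments in a follow-up visit 3 months after the last intervention session". Steps 9g and 9h give the wait-list arm the same two items in the same words.

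**Programme timing (F.4, Overview).** For the AWARE arm: "Participants in this group will receive 8 consecutive weekly sessions to receive the manualized intervention". The wait-list arm receives the same programme, starting 3 months after the AWARE arm starts.

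**Named time points.** Section D lists "assessments at pre-test, 8 weeks, and 3-month follow-up". Section E.5.B, under Adverse Events, evaluates "these adverse events at baseline, 8 weeks, and the 3-month follow-up". Section G.3 will "measure status and severity of the outcomes at baseline, 8 weeks, and 3-month post-test". Section L.2 pays \$20 for each of the 8-week and 3-month evaluations, separately from \$26 per session.

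**Analysis (G.3).** The pilot RCT analysis is by intention to treat: "all women who are randomized will be included for analysis". It uses mixed effects models, and also plans to compare outcome measures between women who drop out and women who complete. The feasibility text expects that "15% of participants will dropout during the 8 week RCT" and that another 5% will be lost at 3 months. Neither figure is split by arm.

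**The concern.** An intention-to-treat comparison needs outcomes from all randomised women at comparable times, whether or not they took up the treatment. Here the operational steps attach outcome collection to a treatment event. They do not say whether the last session is the programme's or the woman's own, and they do not say what happens to a woman who is not there.

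The feasibility text in G.3 adds to this by moving between dropout, adherence, attendance and attrition as if they were one quantity. Leaving the sessions and leaving the assessments are therefore never separated.

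Two things are at stake. Outcomes may be missing or mistimed because of poor engagement, which is the kind of missingness least likely to be harmless. In addition, the listed wait-list visits do not match the untreated comparison at 8 weeks that the Section D hypotheses require. Sections D and I.2 intend the pilot's results to support a larger trial, so a distorted estimate would carry forward. Outcomes not collected at the time cannot be recovered in the analysis.

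**Working it through.** The plan has no figure to reproduce here: G.2 declines a sample size calculation, and no effect size is given. The check is a timeline and a simple illustration.

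**1. When the listed visits fall.** Weeks are counted from the start of the AWARE sessions, with 3 months taken as 13 weeks and the programme's end as week 8.

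| Event | Week |
|---|---|
| AWARE post-treatment visit, programme's last session | 8 |
| AWARE follow-up, 3 months later | 8 + 13 = 21 |
| Wait-list treatment starts | 13 |
| Wait-list treatment ends, and its step 9g visit | 13 + 8 = 21 |
| Wait-list step 9h follow-up | 21 + 13 = 34 |

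- Step 9 lists no wait-list outcome visit after baseline and before the arm's own treatment. The visits it does list, at about weeks 21 and 34, are post-treatment values.
- An AWARE follow-up at week 21 coincides with the end of wait-list treatment. Three months counted from the AWARE start would be week 13, just as wait-list treatment begins. The protocol does not say which is meant.

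**2. An AWARE woman who stops after session 2.**

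- If the anchor is the programme's last session, her visits are due at about weeks 8 and 21, but she is not attending and no step says that she is called.
- If the anchor is her own last session, her visits fall at about weeks 2 and 2 + 13 = 15.

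**3. Illustrative size.** Inputs: 48 women per arm (F.4, step 7) and 15% dropout (G.3). Applying the 15% to the AWARE arm is an assumption.

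- Expected dropouts: 0.15 × 48 = 7.2, about 7, leaving 41.
- Let f be the share of the completers' benefit that dropouts gain, and assume that dropouts and completers would have had similar outcomes untreated. The intention-to-treat effect is then (41 + 7f)/48 of the completers' effect, so the ratio of completers-only to intention-to-treat is 48/(41 + 7f).
- f = 0: 48/41 = 1.17.
- f = 0.5: 48/44.5 = 1.08.
- f = 1: 48/48 = 1.00.

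**4. What the mixed model does.** A likelihood-based mixed model can keep a woman who has a baseline value only, so the planned analysis is not a completers-only analysis. Having no later value from her, it assumes that, given what was observed, her missing outcomes follow those of similar women who were seen. That missing-at-random assumption is doubtful when non-attendance is itself the reason for the missing value.

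**The case against.** The strongest reply is that the intended schedule is clear enough. Several sections name 8 weeks and 3 months. The programme is eight consecutive weekly group sessions, so the last session most naturally means session 8, at about week 8. Assessments are paid separately from sessions (L.2), and H.3 provides for remote assessment. The planned comparison of dropouts with completers presupposes outcome data from dropouts.

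Much of this stands. A reader might infer that the trial has no defined 8-week or 3-month assessment at all. The documents do not support that: the time points are named. What is missing is the date they run from and a statement of who is assessed. The dropout comparison shows an intent to have such data, but no step collects them.

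A reader might also infer that outcomes would be lost in the AWARE arm only. The text does not say so. Steps 9g–h give the wait-list arm the same anchor, and the dropout forecast is not split by arm. One-sided loss would follow only if wait-list women had dated visits before their own treatment, which step 9 does not list.

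Finally, the factor of 1.17 might be read as the expected bias. It is one end of an illustration for a completers-only analysis that the protocol does not plan. It also rests on a dropout figure that does not separate leaving sessions from leaving the study.

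**Conclusion.** The point holds as a gap and an internal inconsistency. Steps 8g–h and 9g–h tie outcome visits in both arms to the last intervention session. Other sections name 8 weeks and 3 months without an origin, and nothing keeps women who stop attending in assessment, despite the intention-to-treat promise. Whom to assess after sessions stop, and when, belongs in the protocol and cannot be left to an analysis plan.

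On size, the firm part is the timeline: the listed wait-list visits fall at about weeks 21 and 34 and cannot serve as untreated 8-week controls. The factor of 1.08 to 1.17 depends on 15% dropout applying to AWARE, on dropouts gaining half the benefit or none, and on a completers-only estimate. With a mixed model the distortion depends on how far missing-at-random fails, and the documents give no basis for a figure.

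The point concerns women who stop attending without being withdrawn. It is a worthwhile, inexpensive correction, and it does not show that the trial's comparison is invalid.

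**What to change.** - Reconcile steps 8g–h and 9g–h with Sections D, E.5.B and G.3. Set the 8-week and 3-month assessment dates in both arms from one stated clock (randomisation or scheduled group start), each with a window. Say whether 3 months counts from that origin or from the end of the 8 weeks, and so whether the wait-list arm is still untreated at that visit.
- State that both assessments are offered to every randomised woman who has not withdrawn consent to assessment, whether or not she attends sessions.
- Where a woman will not come in, use the remote option already described in H.3 for the self-report measures.
- Record stopping sessions and stopping assessments as separate events, and use the two terms consistently in G.3.

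**Cost.** This is mainly wording and scheduling. On the 15% assumption it adds about 7 AWARE assessments per time point: 7 × 2 = 14, or 14 × \$20 = \$280 in fees. If dated wait-list visits are not already planned under Sections D and G.3, they add up to 48 × 2 = 96 assessments, or 96 × \$20 = \$1,920 in fees, plus staff time and any travel payments. No treatment or withdrawal rule needs to change for this.
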